**Tyumen Cardiology Research Center, Tomsk National Research Medical Center, Russian
Academy of Science, Tomsk, Russia**

One-year Cardiac Follow-up of COVID-19 Pneumonia (159)
Study Protocol

13/07/2020

Brief Summary: The primary objective of the study is to assess the cardiac status of COVID-19 pneumonia patients during 1 year after discharge.

Although COVID-19 manifests in most cases with respiratory symptoms, cardiovascular abnormalities are common in hospitalized patients. Patients with cardiovascular risk factors or established disease appear to have a worse prognosis. Myocardial dysfunction could represent a direct manifestation of COVID-19. Investigation of the long-term cardiovascular consequences of COVID-19 is needed. Subjects after COVID-19 pneumonia can present myocardial remodeling for a long time after discharge, even in the absence of prior cardiovascular disease.

Keywords: Covid19; Cardiovascular Disease; Echocardiography

Hypothesis: In patients with COVID-19 pneumonia initiates and aggravates the processes of structural and functional remodeling of the myocardium within 1 year after discharge from the hospital.

Primary Outcome Measure:

Echocardiographic assessment of cardiac function. Echocardiographic assessment of global strain parameters at 3 and 12 months after discharge

[Time Frame: up to one year]

Secondary Outcome Measures:

1. MACCE. Major adverse cardiac and cerebrovascular events: cardiac death, myocardial infarction, or stroke at 3 and 12 months after discharge

[Time Frame: up to one year]

2. Quantitative analysis of parenchymal lung damage. Describe the parenchymal lung damage through a quantitative analysis with chest CT at 3 and 12 months after discharge

[Time Frame: up to one year]

3. Functional exercises capacity assessment. Six-min walk test at 3 and 12 months after discharge

[Time Frame: up to one year]

4. Evaluation of renal function. Measure of creatinine clearance at 3 and 12 months after discharge

[Time Frame: up to one year]

5. Evaluation of inflammation. Analysis for C-reactive protein at 3 and 12 months after discharge

[Time Frame: up to one year]

6. Evaluation of coagulation abnormality. Analysis for activated clotting time at 3 and 12 months

[Time Frame: up to one year]

7. Evaluation of quality of life in first year after discharge. Assessment of the Short Form Health Survey (SF36) at 3 and 12 months after discharge

[Time Frame: up to one year]

The objective of the study is to evaluate the impact of COVID-19 pneumonia on transthoracic echocardiography and other myocardial parameters during 1 year follow-up to monitor cardio-vascular events and predict outcomes.

Population. According to the protocol, the study included men and women ≥ 18 years old with documented COVID-19 pneumonia 3 month \pm 2 week after discharge. The sample size is 380 people (calculation by the Cochran method and Raosoft calculator). The observation period was 12 months \pm 2 weeks. The planned terms of inclusion in the study are the end of December 2020.

Design: The prospective observational study includes men and women ≥ 18 years old who were 3 month \pm 2 week ago discharged after documented COVID-19 pneumonia. Patients were identified from medical information system of local COVID hospital between April and December 2020. The study will be performed in accordance with the International Conference on Harmonization of Good Clinical Practice and the Declaration of Helsinki. The study protocol was approved by the local ethics committee (Approval Number: 159 from 07/23/2020). Every patient is explained the purpose of the study and benefits of participation. If the patient agrees to participate in the study, he signs an informed consent. All patients included have negative results on a swab test at the end of the hospitalization. Exclusion criteria were impossibility to follow up, cancer, tuberculosis. Patients undergo clinical, instrumental and laboratory diagnostics tests during follow-up visits at 3 and 12 month \pm 2 week after discharge, and telephone interview at 6 month after discharge to collect information on health status, outcomes and treatment adjustments.

The study protocol does not provide for a single way for patients managing. If any cardiovascular abnormalities or other disturbances found 3 months after discharge, the therapy carried out.

At the visit of 3 and 12 months, the patient is interviewed (complaints, data of the epidemiological and medical history), clinical examination, anthropometry, measurement of temperature, heart rate, blood pressure, oxygen saturation, dyspnea, myalgia are performed. Based on the data obtained, the diagnosis is specified (arterial hypertension, coronary artery disease, arrhythmias, obstructive pulmonary disease, asthma, obesity, metabolic syndrome, diabetes mellitus, obliterating atherosclerosis and others); the basic therapy is adjusted. Each patient undergoes electrocardiography, general and biochemical blood tests, microalbuminuria test. Lungs CT, echocardiography with myocardial strain assessment, six-minute walk test, assessment of symptoms of stress, anxiety and depressive disorders (PSS-10 GAD7, PHQ9, respectively) are performed. According to diagnosis, patients are divided into groups. Examination at visits of patients in 12 months after discharge is carried out according to the approved examination plan in groups. During the observation, the incidence of adverse cardio-cerebral events (MACCE) and the prognostic value of the structural and functional parameters of the myocardium and blood vessels will be assessed.

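### The Hypothesis and the stated objective ask for an effect of COVID-19 pneumonia that one all-exposed cohort, first scanned at month 3, cannot identify

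*Protocol*

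**What the plan says.** The protocol states its question in three places, and they do not agree.

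- **Brief Summary:** "The primary objective of the study is to assess the cardiac status of COVID-19 pneumonia patients during 1 year after discharge". This is descriptive.
- **Hypothesis:** something, not clearly named in the sentence, "initiates and aggravates the processes of structural and functional remodeling of the myocardium within 1 year after discharge". The natural subject is COVID-19 pneumonia.
- **Objective, just before Population:** to evaluate the "impact of COVID-19 pneumonia on transthoracic echocardiography and other myocardial parameters during 1 year follow-up to monitor cardio-vascular events and predict outcomes". The first half speaks of an effect; the second half adds monitoring and prediction.

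The background in the Brief Summary points the same way as the Hypothesis: "Myocardial dysfunction could represent a direct manifestation of COVID-19".

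The design elements that bear on this are:

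- **Primary Outcome Measure:** "Echocardiographic assessment of global strain parameters at 3 and 12 months after discharge".
- **Population and Design:** 380 adults, all discharged after documented COVID-19 pneumonia. "Patients were identified from medical information system of local COVID hospital".
- **Exclusions (Design):** "Exclusion criteria were impossibility to follow up, cancer, tuberculosis".
- **Between the two visits (Design):** a "telephone interview at 6 month after discharge to collect information on health status, outcomes and treatment adjustments". Therapy follows abnormalities found at month 3.
- **Visit description (last section):** medical history is taken, basic therapy is adjusted, and patients are grouped by diagnosis.

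**The concern.** To say that a disease starts or worsens remodeling is to compare the course with the disease against the course without it. That needs the heart's state before the illness, a comparable group without it, or preferably both. The protocol describes neither. Its groups are formed by diagnosis inside the exposed cohort, so they do not contrast exposure with non-exposure.

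The Hypothesis and objective set the question that the study will report against. As they stand, impaired strain at month 3, or a decline to month 12, could be reported as confirming the Hypothesis, and stable values as refuting it. Neither conclusion follows. The descriptive objective in the Brief Summary can be met, so the protocol carries two different questions and its design supports only one of them.

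**Working it through.** **1. What the month-3 scan contains.** Write strain at month 3 as *Y3 = P + A + B*. *P* is the value before the illness, *A* is the change caused by the illness up to that scan, and *B* is any other change up to that scan. Only *Y3* is observed. *P* is not measured, because no echocardiogram before month 3 is planned or said to be retrieved. It cannot be assumed normal, because prior cardiac disease is not an exclusion. Initiation concerns *A*, and *A* cannot be separated from *P* and *B*.

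**2. What the change contains.** Write *Y12 − Y3 = A′ + C + T + M*. *A′* is any later effect of COVID-19, *C* the course of comorbidity, *T* time and ageing, and *M* therapy adjusted after the month-3 findings. The cohort gives the sum. Without an unexposed course, *A′* cannot be isolated.

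**3. Timing, from the protocol's own windows.** Three months = 365/4 = 91.25 days, and the window is ± 14 days.

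- First echocardiogram: 91.25 − 14 = 77.25 to 91.25 + 14 = 105.25 days after discharge.
- Interval between scans: 365 − 91.25 = 273.75 days. With both windows this is 273.75 ± 28, that is 245.75 to 301.75 days. The contact in between is by telephone.

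These figures locate the missing observation. They do not measure a bias: the attribution problem would remain with a scan at discharge and no comparator.

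**4. Whether sample size helps.** Population attributes the 380 to the Cochran method but gives no inputs. Assuming 95% confidence, *p* = 0.5 and a 5-point margin, *n0* = 1.95996² × 0.25 / 0.05² = 384.1. The finite-population form *n* = *N n0* / (*N* + *n0* − 1) with an assumed *N* of 30,000 gives 379.3, rounded up to 380. The figure is therefore consistent with one-sample precision. This rests on assumed inputs and does not decide the point.

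Precision is not the limit in any case. With all 380 complete, 80% power and a two-sided 5% test, the detectable paired change is (1.960 + 0.842)/√380 = 0.144 SD of the change. As an illustration with assumed values, suppose the observed change is 0.2 SD and all other causes together contribute between −0.2 and +0.2 SD. The implied COVID-19 effect then runs from 0.2 + 0.2 = 0.4 SD down to 0.2 − 0.2 = 0. That range does not depend on *n*.

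**5. What the other recorded data can add.** Medical history and treatment adjustments allow known disease and therapy to be described. They give no prior strain values and no unexposed course.

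**The case against.** The strongest reply is that this is a matter of wording. The objective labelled primary is descriptive, the primary outcome is a measurement at two visits, and no analysis shown in the protocol depends on the causal reading. The Hypothesis has no clear subject, the remark about a direct manifestation is hedged background, and impact can be read loosely in a sentence that goes on to events and prediction. This stands in part: the remedy is indeed mainly wording. But initiation and aggravation are hard to read as description, and the wording governs what the study may conclude.

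A second reply is that the SAP, which is not at hand, could help. It could examine patients with no recorded prior cardiovascular disease, or relate strain to CT lung damage, which is a secondary outcome. This also stands in part. A reader might infer that no analysis could bear on the question at all; the documents do not support that, because both analyses could give supporting evidence of association. Neither would identify the effect: unrecorded or subclinical disease remains possible in the first, and a severity gradient within the exposed can be confounded. Earlier echocardiograms may exist for some patients in the hospital system, but the protocol does not say that any will be used.

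A reader might also infer that the study fails without a control group, or, conversely, that its remaining aims are free of difficulty. Neither is supported. Describing status, counting events and assessing prognosis need no unexposed group. Therapy prompted by month-3 findings nevertheless bears on later change and on the events those findings are meant to predict.

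**Conclusion.** The point holds and should be fixed. The Hypothesis and the effect half of the objective pose a question that the described design cannot answer in either direction, and this is not a detail that an analysis plan can settle. The extent is: no comparator among 380 participants, and no echocardiogram before about day 77 to 105 after discharge. The size and direction of any bias cannot be derived from the documents.

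The conclusion rests on two readings. The first is that COVID-19 pneumonia is the intended subject of the Hypothesis. The second is that the protocol's description of participants and echocardiograms is complete. It does not reach the descriptive primary objective, MACCE incidence or the prognostic aims.

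**What to change.** Reword the Hypothesis and the objective to match the primary objective in the Brief Summary, without narrowing it. For example: *to describe cardiac status (global strain and other structural and functional echocardiographic and myocardial parameters) 3 and 12 months from discharge in patients after COVID-19 pneumonia, to monitor cardiovascular events and to assess the prognostic value of these parameters.*

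Add that any difference between months 3 and 12 will be reported as within-cohort change with therapy adjusted after the month-3 visit, and that neither levels nor change will be attributed causally to COVID-19.

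No visit, test, endpoint or sample size changes. The price is a weaker claim: long-term cardiac consequences are described, not tested.

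If the sponsor keeps the effect question, the protocol must name where the contrast comes from, either earlier echocardiograms or a group without COVID-19 pneumonia. That is a design change and needs data retrieval or further recruitment. Earlier echocardiograms alone would still not separate COVID-19 from comorbidity, treatment and time.

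### MACCE is defined with cardiac death from discharge, but patients enter by consent about 3 months later, so early cardiac deaths cannot be counted

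*Protocol*

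**What the plan says.** Secondary Outcome Measures, item 1, defines MACCE as "Major adverse cardiac and cerebrovascular events: cardiac death, myocardial infarction, or stroke at 3 and 12 months after discharge". The clock named is discharge, and cardiac death is a component at both time points. The Brief Summary sets the same period, to "assess the cardiac status of COVID-19 pneumonia patients during 1 year after discharge", and the objective includes "to monitor cardio-vascular events and predict outcomes".

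The Design section describes a cohort of people who were 3 months ± 2 weeks "ago discharged after documented COVID-19 pneumonia". Entry is by the patient's own agreement: "If the patient agrees to participate in the study, he signs an informed consent". After the 3-month visit there is a "telephone interview at 6 month after discharge to collect information on health status, outcomes and treatment adjustments", and then a visit at 12 months.

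The closing paragraph on visits says that at 3 and 12 months "the patient is interviewed (complaints, data of the epidemiological and medical history"), and that examination and tests follow. It then announces the analysis: "During the observation, the incidence of adverse cardio-cerebral events (MACCE") will be assessed, together with the prognostic value of myocardial and vascular parameters.

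**The concern.** The outcome and the entry rule do not fit together. A composite that includes death is counted from discharge, yet nobody can enter the study without having survived to about month 3. A reader would take 3-month MACCE to include cardiac deaths when it can hold almost none. A 12-month incidence after discharge would be read as covering the whole year, although deaths in roughly its first quarter cannot appear.

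MACCE is the only clinical-event outcome listed, and event monitoring is part of the stated objective. The prognostic analysis is touched too. The myocardial parameters are first measured at the 3-month visit, so an infarction or stroke before that visit is not something they can predict.

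**Working it through.** The protocol states no MACCE rate, so there is no figure of its own to reproduce. Its sample size of 380 (Population) serves below only as a denominator.

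**1. How much of months 0–3 is open to observing a death**

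- Entry window (Design): 3 months ± 2 weeks. Two weeks = 14/30.44 = 0.46 month, so the earliest entry is 3 − 0.46 = 2.54 months.
- Earliest entrants: a death before month 3 can be counted for at most 0.46/3 = 15.3% of the period.
- Average, assuming entry uniform over 2.54 to 3.46 months: half the patients enter before month 3, with a mean of 0.46/2 month left to run. The mean is (0.46/4)/3 = 3.8%. About 96% of months 0–3 therefore lies before entry.

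This step needs no event rates.

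**2. The 12-month figure, if reported from discharge**

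All rates here are assumed. Let R be the true 12-month MACCE risk from discharge, e the share of events falling in months 0–3, f the fatal share of those, and N the proportion dying of non-cardiac causes before entry. Early non-fatal events are taken as counted from history.

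- Early cardiac deaths: F = R·e·f
- Observed risk among those who can enter: (R − F)/(1 − F − N)
- Value of N at which the bias vanishes: e·f·(1 − R)

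With R = 5%:

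| e, f | F | Observed, N = 0 | Understated by | Observed, N = 3% | Understated by | Break-even N |
|---|---|---|---|---|---|---|
| 25%, 25% | 0.3125% | 4.70% | 6.0% | 4.85% | 3.0% | 5.9% |
| 25%, 50% or 50%, 25% | 0.625% | 4.40% | 11.9% | 4.54% | 9.2% | 11.9% |
| 50%, 50% | 1.25% | 3.80% | 24.1% | 3.92% | 21.7% | 23.8% |

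First row worked: (0.05 − 0.003125)/(1 − 0.003125) = 0.0470, and 1 − 0.0470/0.05 = 6.0%.

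Events spread evenly over the year correspond to e = 25%, which gives 6–12% with N = 0. The result depends little on R: with N = 0 the range is 6.1–24.6% for R = 2% and 5.7–23.1% for R = 10%.

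A second parametrisation shows how wide the uncertainty is. Let d be the early cardiac-death risk and s the 12-month MACCE risk among 3-month survivors, ignoring early non-cardiac deaths. The true risk is d + (1 − d)·s, while the cohort shows s. With d = 1% and s = 5% the true risk is 0.01 + 0.99 × 0.05 = 5.95%, so 16% is missed. Over d = 0.25–3% and s = 2–5%, the share missed runs from 4.5% to 60%.

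**3. Counts per 380 enrolled (R = 5%, N = 0, over the rows above)**

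- Uncounted early cardiac deaths, 380·F/(1 − F): 1.2 to 4.8
- MACCE counted from discharge: 380 × 4.70% = 17.9, down to 380 × 3.80% = 14.4
- Of these, early non-fatal, 380·R·e·(1 − f)/(1 − F): 2.4 to 7.2
- Of these, after entry, 380·R·(1 − e)/(1 − F): 14.3 down to 9.6, or 3.8% to 2.5%

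For scale, 17 events in 380 is 4.5%, with a 95% Wilson interval of 2.8% to 7.0%.

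**The case against.** The strongest reply is that the 12-month part is conditional. The phrase about 3 and 12 months is attached to almost every outcome and can be read as a visit schedule, not as a risk interval. An analysis plan that is not shown may count MACCE from entry, and then the 12-month figure has no such bias. That is right as far as it goes, and the 12-month point is limited to reporting from discharge. The protocol does not settle the origin: item 1 says after discharge, the closing paragraph refers only to the observation, and the Population section gives a 12-month observation period without saying from when. No analysis plan can repair the 3-month outcome, because people who died before entry were never enrolled.

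The size is also open to challenge. Every rate is assumed, early non-cardiac deaths could cancel the effect, and consent related to risk could shift it either way. With events spread evenly, the shift of 0.3–0.6 percentage points is smaller than sampling error, and even the largest shift in the table (5.0% to 3.8%) stays inside the interval above. All of this stands, and it limits what can be claimed about month 12.

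Finally, early non-fatal events need not rest on recall alone, since examination, ECG and echocardiography are done at the visit. That is fair, but these too are findings in living patients. Using the hospital information system to identify patients does not help either, because no ascertainment of deaths among the non-enrolled is described.

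**Conclusion.** The concern holds. As written, MACCE at 3 months cannot be the composite that item 1 defines. Apart from deaths between an early entry and month 3, it consists of non-fatal infarction and stroke among survivors. This follows from the protocol's own text and is stated with high confidence.

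A 12-month incidence reported from discharge would omit cardiac deaths before entry and would tend to be too low. The illustrative understatement is 6–24%, or 3–22% if 3% die early of non-cardiac causes. The direction is likely but not certain, and the true size is unknown. Counted from entry, the 12-month figure does not have this problem. The point should be fixed, but it leaves the primary strain outcome untouched.

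**What to change.** In Secondary Outcome Measures, item 1, and in the closing paragraph on visits:

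- State that the MACCE risk period starts at the entry (3-month) visit. Report incidence from that visit to month 12, described as conditional on being alive and enrolled at about 3 months.
- Replace the 3-month MACCE outcome by a separate count of infarction or stroke between discharge and entry, labelled as non-fatal history among survivors.
- As part of the same change, use only events after the 3-month visit as outcomes in the prognostic analysis.

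The cost is protocol wording and one time origin. Events known at the 3-month visit can be separated from those learned later, so no new data are needed. The price is fewer counted events: on the assumptions above, about 10 to 14 from entry to month 12 instead of 14 to 18, with about 2 to 7 early non-fatal events reported separately.

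### Does a sample size of 380, stated without inputs, leave the prognostic aim unsupported?

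*Protocol*

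**What the plan says.** The Population paragraph gives the number and its source in one sentence: "The sample size is 380 people (calculation by the Cochran method and Raosoft calculator". No input to the calculation appears there or elsewhere in the protocol.

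The protocol then describes several things to be done with these patients:

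- The Primary Outcome Measure is "Echocardiographic assessment of global strain parameters at 3 and 12 months after discharge". The hypothesis concerns myocardial remodeling over the year.
- The first Secondary Outcome Measure is "Major adverse cardiac and cerebrovascular events: cardiac death, myocardial infarction, or stroke at 3 and 12 months after discharge". No expected rate is given.
- The objective ends with the intention "to monitor cardio-vascular events and predict outcomes".
- The description of the visits closes by saying that MACCE incidence, and "the prognostic value of the structural and functional parameters of the myocardium and blood vessels will be assessed". The same paragraph says "According to diagnosis, patients are divided into groups", and links those groups to the examination plan for the 12-month visit.

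Under Design, patients are enrolled about three months after leaving hospital, and "Patients undergo clinical, instrumental and laboratory diagnostics tests during follow-up visits at 3 and 12 month". The first study echocardiogram is therefore at month 3.

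**The concern.** Two features together look like a defect. First, the protocol itself fixes the sample size and says it was calculated, yet a reader cannot repeat the calculation. Cochran's method sizes a sample for estimating a proportion, while the primary outcome is continuous. Second, one number stands behind aims with different needs. Estimating mean strain depends on the number of patients. Predicting MACCE depends on the number of events, and MACCE is a narrow composite. A month-3 echocardiogram can predict only what happens afterwards, about nine months up to the last visit.

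If events turned out to be few and several echocardiographic parameters were tried as predictors, most real associations would be missed, and those reaching significance would tend to be overstated. A reader might then credit the prognostic result with the same support as the strain result.

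**Working it through.** **1. The stated figure.** It cannot be reproduced from the document, because "calculation by the Cochran method and Raosoft calculator" is all that is given. With common inputs, all assumed (95% confidence, proportion 50%, margin 5 points), Cochran's formula gives

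n0 = z² p(1 − p) / e² = 1.96² × 0.25 / 0.05² = 384.1,

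which is (384.1 − 380)/380 = 1.1% above the stated number. The finite-population correction n0 / (1 + (n0 − 1)/N) returns exactly 380, after rounding up, for N between about 28,000 and 35,000. For N = 30,000 it is 384.1 / (1 + 383.1/30,000) = 379.3, rounded up to 380. The protocol mentions no such N, so this shows only that 380 is plausible, not how it arose.

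**2. The primary outcome.** The 95% half-width for mean strain at one visit is 1.96/√380 = 0.10 SD. If 20% were lost (assumed), 304 remain and it is 1.96/√304 = 0.11 SD. For the change from month 3 to month 12 it is 1.96 √(2(1 − ρ)) / √380, which gives 0.12, 0.10 and 0.08 SD for assumed correlations ρ of 0.3, 0.5 and 0.7. The change detectable with 80% power is 0.17, 0.14 and 0.11 SD. The primary outcome is well served.

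**3. The prognostic aim, read as prediction of MACCE.** Assume a Cox model with one unadjusted continuous predictor, two-sided 5%, 80% power and no loss. The events needed are

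D = (1.960 + 0.842)² / (ln HR)².

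- HR 1.5 per SD: 7.849 / 0.1644 = 47.7, so 48 events, or 48/380 = 12.6%.
- HR 2.0 per SD: 7.849 / 0.4805 = 16.3, so 17 events, or 17/380 = 4.5%.

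The protocol gives no rate, so a range is needed. The detectable HR is exp(2.802/√events). Power for HR 1.5 is Φ(√events × ln 1.5 − 1.96).

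| Assumed MACCE rate after month 3 | Events in 380 | Detectable HR per SD | Power for HR 1.5 |
|---|---|---|---|
| 2% | 7.6 | 2.76 | 20% |
| 5% | 19 | 1.90 | 42% |
| 10% | 38 | 1.58 | 71% |
| 12.5% | 47.5 | 1.50 | 80% |

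For HR 2.0, simulated power at a 5% rate is 83%. The answer runs from poor to adequate depending on two quantities, the event rate and the hazard ratio, and the protocol states neither.

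**4. If the outcome to be predicted were continuous**, such as walking distance, 380 patients would detect a correlation of tanh(2.802/√377) = 0.14, and the difficulty would disappear.

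**5. Groups by diagnosis.** The text uses the groups to organise the 12-month examination. It states no comparison of strain between them, so there is no group contrast for 380 to be tested against.

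**The case for a change.** The best case for a change runs as follows. A protocol that claims a calculation should let it be checked, and this is not a detail to hand to an analysis plan. Prediction is part of the objective, nothing labels it exploratory, and MACCE is the only outcome named beside it. The 12.6% figure is a favourable one: 90% power needs 64 events, and a squared correlation of 0.2 with other covariates needs 60. A sentence giving the inputs and calling the prognostic work exploratory would cost no patients.

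Part of this stands. The inputs are missing, MACCE is the natural reading, and precision would be poor if events were rare. It does not amount to a fault in the plan. MACCE is a secondary outcome and the hypothesis is about remodeling; sizing a study without reference to its secondary aims is ordinary. Nowhere is prediction presented as confirmatory, so an exploratory label would take away nothing that was claimed. The number of predictors, the choice of strain parameter and the modelling are matters a protocol commonly leaves to the analysis plan, which is not at hand. Counting only events after the month-3 echocardiogram is what an analyst would do in any case.

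Nor do the stronger remedies improve matters. Stating that 380 was chosen for strain would be a guess about its history. A floor of 48 events before fitting a multivariable model or deriving a cut-off borrows a power threshold for one unadjusted predictor, and 60 events are already needed in the covariate example above. Enlarging the study to 47.74/0.05 = 955 patients at a 5% rate, or 47.74/0.02 = 2,388 at 2%, would mean about 2.5 to 6 times the patients for a secondary aim.

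**Conclusion.** No change to the plan is called for. The basis of 380 is under-reported, but the number is not shown to be wrong: it is within about 1% of a common Cochran result, and it gives a half-width near 0.10 SD for mean strain at one visit. For MACCE prediction, the 48 events (12.6%) at a hazard ratio of 1.5 per SD and the 17 (4.5%) at 2.0 are correct under their assumptions of 80% power, two-sided 5%, one unadjusted predictor and no loss. They cannot be set against any rate, effect or power in the protocol, so no shortfall is demonstrated. This is a gap in detail that analysts fill sensibly by giving event counts and confidence intervals with any prognostic result and reading it as exploratory. The conclusion would differ if the protocol had promised a stated power for prediction or presented it as confirmatory, and it does neither.

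### Do the April–December 2020 identification period, the 3-month entry rule and the end-December close of inclusion contradict each other?

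*Protocol*

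**What the plan says.** Four statements in the Protocol bear on the enrolment calendar.

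- **Entry rule (Design).** Participants are adults "who were 3 month \pm 2 week ago discharged after documented COVID-19 pneumonia". The Population paragraph gives the same timing.
- **Inclusion date (Population).** "The planned terms of inclusion in the study are the end of December 2020". The sentence does not say whether this is the opening or the close of inclusion.
- **Identification (Design).** "Patients were identified from medical information system of local COVID hospital between April and December 2020". No day of the month is given, and no range of discharge dates appears anywhere.
- **Approval and consent (Design).** Ethics approval is recorded as "Approval Number: 159 from 07/23/2020", that is, 23 July 2020. On consent: "If the patient agrees to participate in the study, he signs an informed consent".

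The title page is dated 13 July 2020. The planned size, 380, is attributed to a Cochran calculation and a web calculator. It does not depend on any of these dates.

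**The concern.** On a quick reading, April to December 2020 looks like the range of discharges from which the cohort is drawn. Entry comes about three months after discharge, so the latest discharges in that range would become eligible only in 2021, after inclusion had apparently ended. At the other end, the earliest April discharges would pass through their window before the ethics approval.

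If that were so, the real source of the 380 patients would be narrower than the stated one. Either autumn and winter discharges would be listed but never enrolled, or inclusion would run past its stated end. A further worry is that early patients might be examined before approval or outside the window. That would matter because the 3-month visit is the first of only two assessments of global strain, the primary outcome, and of nearly all the secondary outcomes.

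**Working it through.** The Protocol gives no derived date to reproduce, so the check is calendar arithmetic followed by a comparison of readings.

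**Inputs.** Entry at discharge + 3 months ± 14 days (Population, Design); approval on 23 July 2020 (Design); close of inclusion on 31 December 2020 (Population; an assumption, since the sentence does not say close); span of 1 April to 31 December 2020, 275 days (Design; the first and last days are assumed).

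**Reading A: the span gives discharge dates.**

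1. Last discharge able to enter: discharge + 3 months − 14 days ≤ 31 December 2020.
   - 14 October → 14 January 2021 − 14 days = 31 December 2020: just possible.
   - 15 October → 1 January 2021: too late.
   - 31 December → window 17 March to 14 April 2021.
2. First discharge still in window at approval: discharge + 3 months + 14 days ≥ 23 July 2020.
   - 8 April → 8 July + 14 days = 22 July: one day short.
   - 9 April → 23 July: just possible.
3. Days lost at the end: 15 October to 31 December = 17 + 30 + 31 = 78, and 78/275 = 28%.
4. Days lost at the start: 1 to 8 April = 8.
5. Days usable: 275 − 78 − 8 = 189.
6. Counting 3 months as 90, 91 or 92 days moves the cut-offs only to 14–16 October and 8–10 April.

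The early loss of 8 days needs discharges on 1 to 8 April. The text says only April, and a range starting on 9 April would satisfy it.

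**Reading B: the span gives the dates of the record search.** This is what the verb in the identification sentence says. Two examples:

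- A patient found in the records on 1 December and discharged on 15 September has a window of 15 December ± 14 days, that is, 1 to 29 December 2020. Entry before the close is possible.
- A patient found at discharge on 20 April has a window of 20 July ± 14 days, that is, 6 July to 3 August 2020. Entry from 23 July to 3 August is possible.

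On this reading no two dates conflict.

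**Effect on the data.** Each patient's window is counted from that patient's own discharge. On Reading A with a December close, later discharges simply do not enter. If inclusion ran on instead, it would end by 14 April 2021. In both cases everyone included is first seen at 3 months ± 2 weeks, so the interval to the 12-month visit is unaffected.

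**The case for a change.** The strongest case for a change is that neither reading is clean. Reading A loses 28% of the calendar span. Reading B has the search starting in April, about three months before the protocol date and the approval. Reading the end-December sentence as the opening of inclusion makes matters worse: only discharges from 17 September would still be in window on 31 December, so on Reading A 1 April to 16 September, 169 of 275 days (61%), would be lost. The discharge range also defines the cohort, and that belongs in a protocol. Finally, a document dated 13 July cannot have been written that day if it reports a 23 July approval and speaks in the past tense of identification through December.

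Some of this stands. The period is not defined, and the text needs a version date later than the approval it reports.

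The rest does not carry. Finding patients in a hospital's records is not enrolment; the Protocol ties participation to signed consent and nowhere says that anyone was examined before 23 July. The opening-date reading is the less natural one, and the conflict it creates is a reason to prefer the close. There is one source hospital, so different sites would not build different cohorts from the same sentence. The title-page date may be that of the version submitted for approval, with the approval details added later.

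**Conclusion.** No change to the plan is needed. The cut-offs of about 14 October and 9 April are correct, but they conflict with the Protocol only if April to December 2020 is taken as a discharge range, which the text does not say. Even then the size is at most 78 of 275 calendar days at the end and 8 at the start. These are days, not patients, because the Protocol gives no discharge counts by date. They also rest on 31 December being the close of inclusion and on nobody being included before approval.

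A team following the text would search the hospital system, invite those who fall 3 months ± 2 weeks after discharge, and stop at the end of December 2020. That gives a coherent cohort with a common baseline. Patients outside the window are not included, so the paired comparisons are not blurred. The study report can give the actual discharge and inclusion dates. What is left is a missing definition that analysts can fill sensibly and a clerical slip in the document date. Neither would alter an estimate or a conclusion.
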